Previous studies have demonstrated that both thoracic epidurals and paravertebral blocks provide adequate analgesia for VATS. Thoracic epidurals provide excellent pain relief but are associated with hypotension and more nausea/vomiting. Paravertebral catheters have the advantage of having a lower side effect profile than thoracic epidurals. Paravertebral blocks have also been shown to improve respiratory function after surgery. Single shot paravertebral blocks have been described as providing adequate post-VATS pain control, despite a shorter duration of action compared to catheter. In order to evaluate the effectiveness and the side effects of the different pain modalities for post-VATS pain control, we will compare these three different methods of pain blocks:

- 1)single shot paravertebral block
- 2)paravertebral catheters
- 3)thoracic epidural

Rationale and Specific Aims

All of the pain control modalities allow for titration and continuous infusion of local anesthetic to achieve adequate pain control for the duration that the catheter remains in place, except for the single shot paravertebral block. The specific aim of the study is to compare the difference between the three pain blocks in achieving the following:

1. Improved postoperative pain scores
2. Decreased opioid requirements
3. Improved patient satisfaction scores
4. Decreased opioid side effects (Nausea, sedation, ileus, urinary retention, respiratory depression)

The primary endpoint of this study will be VAS pain score. The VAS scores will be taken with both rest and movement.

The secondary endpoint includes intravenous opioid consumption and opioid side effects (nausea, sedation, ileus, urinary retention, respiratory depression). The IV and PO opioid doses will be quantified at 1, 24, 48, and 72 hours. We will also measure postoperative nausea and sedation scores at 1, 24, 48, and 72 hours. We will also measure time to first bowel movement, incidence of urinary retention, incidence of respiratory depression, and time to discharge. If subjects are discharged prior to completing the 72-hour endpoints, efforts will be made to contact them and obtain data points. If unable to be reached, or unable to collect data, we will not consider these deviations since it will not change the integrity of the study data.

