2.0 Inclusion/Exclusion Criteria

Inclusion criteria:

- Pt undergoing VATS procedure at Indiana University Hospital
- ASA 1,2,3 or 4
- Age 18 or older, male or female
- Desires Regional anesthesia for postoperative pain control

Exclusion criteria:

- Any contraindication for Thoracic Epidural or Paravertebral block
- History of substance abuse in the past 6 months
- Patient staying intubated after surgery
- Known allergy or other contraindications to the study medications , which include dilaudid, bupivacaine, ropivacaine

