3.0 Enrollment/Randomization

All VATS cases scheduled by thoracic surgeons at IU Health University Hospital will be identified. The subjects will be contacted face-to-face prior to surgery. They will be informed about the study and all questions will be answered. The potential subjects will be given a copy of the informed consent form and authorization form. The subjects will then be contacted face-to-face in POCU on the day of surgery and if participation is agreed, written consent will be taken.

A total of 120 subjects will be randomized by a computer program into three groups (40 per group):

1. US- Guided Paravertebral Catheter (PVB-A)- The Alaris pump will deliver 0.2% Ropivacaine at a rate of 10 ml/hr
2. Single Shot Paravertebral Block- placed by ultrasound using 0.2% Ropivacaine bolus.
3. Thoracic Epidural- The Alaris pump will deliver an epidural mixture of 0.125% bupiv/hydromorphone

Randomization will be stratified by prior opioid experience (opioid naïve or opioid tolerant). Separate randomization lists will be used for the two strata.

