4.0 Study Procedures

All the thoracic epidurals and ultrasound-guided paravertebral blocks will be placed preoperatively. All procedures will be done using sterile technique with masks, hats, and sterile gloves. All procedures will be placed under the supervision of the attending anesthesiologist on the acute pain service or the attending anesthesiologist in the VATS room.

Thoracic epidurals will be placed using the Arrow thoracic epidural kit. Fentanyl and midazolam will be given prior to epidural placement. The epidural will be placed at the appropriate level to cover the entry site for the VATS procedure. Placement will be determined by anatomical landmarks. The epidural needle will be advanced toward the epidural space utilizing a Paramedian approach and loss-of-resistance technique. A sterile catheter will then be secured in place and the epidural infusion will be started at the end of the case.

Ultrasound guided paravertebral catheter and single shot paravertebral block will be accomplished using an ultrasound transducer at the thoracic level. This will be done using an in-plane or out-of-plane approach, at the discretion of the anesthesia staff performing the procedure. Then a needle will be inserted the needle into the paravertebral space and local anesthetic injected. Then a catheter will be placed within the injectate and secured in place in the case of the paravertebral catheter. The 0.2% Ropivacaine will be delivered by OnQ pump.

General anesthesia will be induced and the patient will be placed in the lateral position for the VATS procedure. The patients will be intubated with dual lumen endotracheal tubes and placed on one-lung ventilation for the procedure.

All patients will receive intravenous patient-controlled analgesia (PCA hydromorphone) post-operatively for breakthrough pain. Usual standard of care for pain control following a VATS procedure include scheduling PO acetaminophen and PO oxycodone PRN on POD 1 once patients tolerate diet.

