6.0 Study Withdrawal/Discontinuation

The patient can withdraw from the study at any time by contacting the research team or acute pain anesthesia resident. In such an event, the catheter will be removed immediately, provided no anticoagulants had been administered. Patient may still have access to Alaris pump and will have access to all the IV and oral pain medications. Anesthesia acute pain team will continue to follow the patient for 24 hours. 24 hours after catheter removal, anesthesia acute pain team will sign off and all further pain management will be done by the primary team.

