7.0 Statistical Considerations

Primary outcome: VAS score at 24 and 48 hours

Primary Research Hypothesis: Thoracic epidural and Ultrasound guided paravertebral block with continuous catheter will provide lower pain scores compared to single shot paravertebral block.

Secondary outcomes: Opioid usage after 1, 24, 48 and 72 hours. Pain scores using VAS at rest and on movement at 1, 24, 48 and 72 hours. Patient satisfaction scores at 24 and 48 hours. Nausea scores at 1, 24, 48 and 72 hours. Sedation scores at 1, 24, 48 and 72 hours. Time to first bowel movement, incidence of urinary retention, and incidence of respiratory depression will be recorded as well.

Secondary Research Hypotheses: Thoracic epidural anesthesia and Ultrasound guided paravertebral catheter will show improved pain control, improved patient satisfaction scores, and decreased nausea and sedation scores compared to single shot paravertebral.

Statistical analysis will be performed using a standard statistical program (SAS or SPSS). All data will be summarized (means, standard deviations, standard errors, and ranges for continuous variables; frequencies and percentages for categorical variables) by group. Demographic data will be compared between the four groups using ANOVA or chi-square tests as appropriate. The primary outcome, VAS at 24 and 48 hours, will be compared between the groups using repeated measures ANOVA; the model will include fixed effects for group, time, and the group by time interaction and random effects to allow correlations between the two times and different variances for the two times. Pain and satisfaction scores and opioid usage over time will be analyzed using repeated measures ANOVA. Nausea and sedation scores will be compared between groups at each time point using Mantel-Haenszel chi-square tests for ordered categorical data. Distributions of the continuous variables will be examined, and a transformation of the data (e.g. natural logarithm) or nonparametric tests will be used as necessary. A 5% significance level will be used for all comparisons.

Based on prior studies, the coefficient of variation for the VAS score at 24 and 48 hours is estimated to be 0.70. With a sample size of 40 per group the study will be able to detect a 60% decrease in VAS score between any two groups, assuming two-sided tests each conducted at a 5% significance level.

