9.0 Follow-up and Record Retention

The study will start at the beginning of 2017 and will end when a sample size of 120 subjects is achieved. The estimated time frame to enroll 120 study subjects is 24 months. After 120 subjects have been enrolled, the study will be stopped and the data collected will be analyzed using statistical methods.

At the end of the study, all study papers with patient identifiers will be shredded and only data without any patient identifiers will be retained by the research team for an indefinite time.

References

Bottiger, B. A., Esper, S. A., & Stafford-Smith, M. (2013, December). Pain management strategies for thoracotomy and thoracic pain syndromes. In *Seminars in cardiothoracic and vascular anesthesia* (p. 1089253213514484). SAGE Publications.

Daly, D. J., & Myles, P. S. (2009). Update on the role of paravertebral blocks for thoracic surgery: are they worth it? *Current Opinion in Anesthesiology*, 22(1), 38-43.

Davies, R. G., Myles, P. S., & Graham, J. M. (2006). A comparison of the analgesic efficacy and side-effects of paravertebral vs epidural blockade for thoracotomy—a systematic review and meta-analysis of randomized trials. *British journal of anaesthesia*, 96(4), 418-426.

El-Morsy, W. Z. (2013). Thoracic epidural analgesia versus parenteral morphine for post-thoracotomy pain relief. *Ain-Shams Journal of Anaesthesiology*, 6(2), 180.

Fibla, J. J., Molins, L., Mier, J. M., Sierra, A., Carranza, D., & Vidal, G. (2011). The efficacy of paravertebral block using a catheter technique for postoperative analgesia in thoracoscopic surgery: a randomized trial. *European Journal of Cardio-Thoracic Surgery*, 40(4), 907-911.

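### Does the sample-size statement need reworking because it gives no power, scale, reference mean for the CV or allowance for loss?

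*Combined protocol and SAP*

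**What the plan says.** The sizing argument is in the last paragraph of section 7.0 (Statistical Considerations). Citing prior studies, it states that "the coefficient of variation for the VAS score at 24 and 48 hours is estimated to be 0.70". It then claims that, with 40 per group and two-sided tests each at 5%, "the study will be able to detect a 60% decrease in VAS score between any two groups".

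Section 3.0 randomizes the same number: "A total of 120 subjects will be randomized by a computer program into three groups (40 per group"). Section 9.0 ends recruitment at that total: "After 120 subjects have been enrolled, the study will be stopped and the data collected will be analyzed using statistical methods".

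Several provisions allow patients or data to be lost after randomization:

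- Section 2.0 lists as an exclusion "Patient staying intubated after surgery", while section 4.0 says "All the thoracic epidurals and ultrasound-guided paravertebral blocks will be placed preoperatively".
- Section 6.0 says "The patient can withdraw from the study at any time".
- Rationale and Specific Aims, within section 1.0, says "If subjects are discharged prior to completing the 72-hour endpoints, efforts will be made to contact them and obtain data points", and does not count a failure to obtain them as a deviation.

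The primary outcome is VAS at 24 and 48 hours. It is analysed by a repeated measures model with group, time and their interaction. A transformation or nonparametric test is permitted if the distributions call for it.

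**The concern.** A detectable difference means little without the power at which it is detectable, and no power appears anywhere in the document. Four other inputs are also open: the mean to which the CV refers, whether the 60% is on the raw or the log scale, which time point or contrast is being sized, and how many of the 40 are expected to be evaluable. This sentence is the only justification for 120 patients.

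The omission seems to have a practical side. The 40 in the calculation is the number randomized, so nothing has been added for loss. Yet a block placed before surgery can be followed by an exclusion known only after surgery, and patients may withdraw. If the intended power were 95% there would be little room for loss, and if it were 80% there would be plenty. The reader cannot tell which applies. At stake would be an undersized trial whose plan does not reveal it.

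**Working it through.** **Inputs.** From section 7.0: CV 0.70, 40 per group, a 60% decrease, two-sided 5% per test with no multiplicity adjustment. Not given: power, scale, reference mean, contrast, evaluable number. The plan's 60% therefore cannot be reproduced as the solution of a power equation. What can be done is to compute the power it implies under each reading.

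**Method.** Two-sample t-test with n evaluable per group. Standardized effect d = difference / SD; noncentrality = d × √(n/2); degrees of freedom 2n − 2; power = probability that the noncentral t exceeds the two-sided 5% critical value.

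**Reading A: untransformed, common SD = 0.70 × the higher mean, one time point.** d = 0.60 / 0.70 = 0.857. With n = 40, noncentrality = 0.857 × √20 = 3.83 on 78 degrees of freedom, and power is 96.6%.

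| Evaluable per group | Power for a 60% decrease |
|---|---|
| 40 | 96.6% |
| 37 | 95.3% |
| 36 | 94.8% |
| 30 | 90.4% |
| 29 | 89.4% |
| 23 | 81.1% |
| 22 | 79.3% |

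The smallest sufficient numbers are 37, 30 and 23 at 95%, 90% and 80% power. Out of 40, the loss absorbed is 40 − 37 = 3, 40 − 30 = 10 and 40 − 23 = 17.

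**Reading B: log scale.** SD = √ln(1 + 0.70²) = √ln 1.49 = 0.631; difference = −ln 0.40 = 0.916; d = 1.451.

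**Reading C: untransformed, CV 0.70 in each group.** The SDs are 0.70 and 0.70 × 0.40 = 0.28 in units of the higher mean; root mean square √((0.49 + 0.0784)/2) = 0.533; d = 0.60 / 0.533 = 1.125.

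**Reading D: as A, but the contrast is the mean of the 24- and 48-hour scores.** With equal variances and correlation ρ, the SD is 0.70 × √((1 + ρ)/2). The document gives no ρ; the range 0.3 to 0.7 is an assumption. d runs from 1.063 (ρ = 0.3) to 0.930 (ρ = 0.7).

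| Reading | Power with 40 | Needed at 95 / 90 / 80% | Loss absorbed at 95 / 90 / 80% |
|---|---|---|---|
| A | 96.6% | 37 / 30 / 23 | 3 / 10 / 17 |
| B | above 99.9% | 14 / 12 / 9 | 26 / 28 / 31 |
| C | 99.9% | 22 / 18 / 14 | 18 / 22 / 26 |
| D, ρ = 0.3 | 99.7% | 24 / 20 / 15 | 16 / 20 / 25 |
| D, ρ = 0.7 | 98.4% | 32 / 26 / 20 | 8 / 14 / 20 |

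**Sensitivity to the CV, reading A, n = 40.** The 60% keeps at least 90% power up to a CV of 0.81 and at least 80% up to 0.94. At an assumed CV of 1.0 its power is 75.5%.

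**Smaller effects, reading A, n = 40.** The detectable decrease is 44.4%, 51.4% and 57.1% at 80%, 90% and 95% power. The stated 60% lies above all three, so the claim is conservative on its own inputs.

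**The case for a change.** The strongest case for a change is that power is a basic element of any sample-size statement, and stating it would take only a sentence or two. The document itself provides for loss after randomization while making no allowance for it, and the tolerable loss varies so widely across readings that the text does not fix an answer. The omission is real, and that much stands.

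The stronger forms do not. The 60% can be checked in the sense that matters, because it is bounded from below at 96.6% power across the literal readings. The figures 3, 10 and 17 belong to reading A, the least forgiving of those tried, and the scale and SD convention move the tolerance as much as the power does. A less literal reading, a ratio of 1.6 on the log scale, would need 48, 39 or 30 per group at 95%, 90% or 80% power. But that is a decrease of 1 − 1/1.6 = 37.5%, not the 60% that the plan claims.

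The practical effect is also unproven. Replacement of lost patients is not addressed, which differs from its being ruled out; nothing says whether a patient excluded for remaining intubated counts towards 120. Section 6.0 does not say that data from withdrawn patients are discarded. The discharge provision concerns the 72-hour endpoints, so it reaches the primary scores only if discharge is earlier than 48 hours. The repeated measures model can also use a patient with one of the two scores. No loss rate is given for any of these routes.

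**Conclusion.** The sample-size sentence is incomplete but not shown to be wrong. With a CV of 0.70, two-sided 5% tests and 40 evaluable per group, a 60% decrease has at least 96.6% power on every literal reading tried. On the most demanding one, a group could lose 10 of its 40 patients and still have 90% power. Stating the power, scale, reference mean and evaluable number would make the sentence reproducible. It would change neither the 120 patients, nor the primary model, nor any result or conclusion. This is a reporting gap that a competent reader can bound, so no change to the plan is called for.

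The conclusion rests on the stated CV of 0.70 and on a 60% decrease being the effect of interest. It does not show that the trial is well powered for smaller effects: on reading A, 80% power is reached only for decreases of about 44% or more.

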8.0 Privacy/Confidentiality Issues

All study papers containing patient identifiers will be kept in each subjects confidential study file accessible to only the research team. All records will be kept in a locked room in a locked cabinet that only authorized staff enters. Collected data from each enrolled participant will be recorded on Redcap which is a secure web-based data collection tool. At the end of the study, all electronic information and paperwork containing patient identifiers will be deleted or shredded.

9.0 Follow-up and Record Retention

The study will start at the beginning of 2017 and will end when a sample size of 120 subjects is achieved. The estimated time frame to enroll 120 study subjects is 24 months. After 120 subjects have been enrolled, the study will be stopped and the data collected will be analyzed using statistical methods.

At the end of the study, all study papers with patient identifiers will be shredded and only data without any patient identifiers will be retained by the research team for an indefinite time.

References

Bottiger, B. A., Esper, S. A., & Stafford-Smith, M. (2013, December). Pain management strategies for thoracotomy and thoracic pain syndromes. In *Seminars in cardiothoracic and vascular anesthesia* (p. 1089253213514484). SAGE Publications.

Daly, D. J., & Myles, P. S. (2009). Update on the role of paravertebral blocks for thoracic surgery: are they worth it? *Current Opinion in Anesthesiology*, 22(1), 38-43.

Davies, R. G., Myles, P. S., & Graham, J. M. (2006). A comparison of the analgesic efficacy and side-effects of paravertebral vs epidural blockade for thoracotomy—a systematic review and meta-analysis of randomized trials. *British journal of anaesthesia*, 96(4), 418-426.

El-Morsy, W. Z. (2013). Thoracic epidural analgesia versus parenteral morphine for post-thoracotomy pain relief. *Ain-Shams Journal of Anaesthesiology*, 6(2), 180.

Fibla, J. J., Molins, L., Mier, J. M., Sierra, A., Carranza, D., & Vidal, G. (2011). The efficacy of paravertebral block using a catheter technique for postoperative analgesia in thoracoscopic surgery: a randomized trial. *European Journal of Cardio-Thoracic Surgery*, 40(4), 907-911.

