All patients will receive a phone survey 6 months after surgery to assess for pain and quality of life. If the 6 month questionnaire is unable to be completed, we will not consider this a deviation since it will not affect the integrity of the study data. However, every attempt will be made to complete a follow up questionnaire.

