Opioid usage at 1,24,48,72 hours after the block will be recorded by a member of the research team. Pain scores at rest and on movement (knee flexion) will be measured by the investigator using Visual Analog Scale (VAS). Nausea will be measured using a categorical scoring system (none=0; mild=1; moderate=2; severe=3). Sedation scores will also be assessed by a member of the study team using a sedation scale (awake and alert=0; quietly awake=1; asleep but easily roused=2; deep sleep=3). All these parameters will be measured at 1, 24, 48 and 72 hours after the epidural or PVB. Patients will be encouraged to ambulate on postoperative day 1 under supervision.

All catheters will be removed by APS (Acute Pain Service) while patients are still in the hospital. APS will continue to follow the patients until catheter removal. Patient's hospital length of stay and readmission rate will be recorded from NSQIP (National Surgical Quality Improvement Program) data.

All patients will receive a phone call 6 months after surgery for assessment for chronic post-surgical pain. Patients will be assessed by a member of the research team over the phone. They will be assessed on their pain score and narcotic usage by using the Brief Pain Inventory. Study participation will conclude after the 6 month follow questionnaire has been completed.

5.0 Reporting of Adverse Events or Unanticipated Problems involving Risk to Participants or Others

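### Section 9.0 ends the study at the 120th enrolment, which conflicts with the 6-month call promised to every patient and leaves unclear when contact details may be destroyed

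*Combined protocol and SAP*

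**What the plan says.** Section 9.0 says that the study "will end when a sample size of 120 subjects is achieved", and then: "After 120 subjects have been enrolled, the study will be stopped and the data collected will be analyzed using statistical methods". It also gives the expected pace: "The estimated time frame to enroll 120 study subjects is 24 months".

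The same section says that, once the study is over, "all study papers with patient identifiers will be shredded". Section 8.0 adds that electronic information carrying identifiers is deleted at that point too. Neither section gives a calendar date or a patient-level milestone for the destruction.

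Other sections set a later end for each patient. Section 1.0, under Rationale and Specific Aims: "All patients will receive a phone survey 6 months after surgery to assess for pain and quality of life". Section 4.0: "All patients will receive a phone call 6 months after surgery for assessment for chronic post-surgical pain", followed by "Study participation will conclude after the 6 month follow questionnaire has been completed". Section 5.0 likewise treats the 6-month telephone questionnaire as the close of participation. Section 1.0 names the effect of the techniques on pain at 6 months as an aim.

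Section 1.0 also says that an uncompleted 6-month questionnaire is not a deviation, but commits staff to trying to obtain it. Section 7.0 lists no 6-month outcome and plans no analysis of one.

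**The concern.** The only statement of when the study as a whole ends is the 120th enrolment. The last patient enrolled cannot have a 6-month call before that moment, and neither can anyone enrolled in the preceding 6 months. Section 9.0 is the section on follow-up, yet it provides no follow-up period after the last enrolment, and no other section does.

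The identifiers make this more than loose wording. A telephone call needs a name and a number. If staff take the end of the study from Section 9.0 and then apply the destruction rules in Sections 8.0 and 9.0, the means of making the remaining calls is gone and cannot be recovered.

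At stake is the 6-month pain aim. The patients affected would be those treated latest, so the 6-month results would describe only the earlier part of enrolment, with fewer patients per group.

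**Working it through.** **Inputs**

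- Total sample: three groups of 40 (Section 3.0). 3 × 40 = 120, which agrees with Section 9.0.
- Accrual period T: 24 months, itself an estimate (Section 9.0).
- Follow-up: 6 months after surgery, all patients (Sections 1.0 and 4.0).
- Enrolment and surgery are taken as the same day, since Section 3.0 has consent signed on the day of surgery.
- Accrual pattern: not given in the documents. Even accrual is assumed first, then varied.

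The plan states no figure for calls falling after the stop, so beyond the total of 120 there is none to reproduce.

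**Formula.** If F(t) is the fraction enrolled by month t, the share of patients who have not reached 6 months when the 120th enrols is 1 − F(T − 6). With even accrual this is 6/T.

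**Base case.** 120/24 = 5 patients per month. 5 × 6 = 30 patients in the last 6 months. 30/120 = 25%, on average 30/3 = 10 per group.

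**Other accrual shapes, T = 24, so F is evaluated at month 18**

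- Rate rising linearly from zero: F = (18/24)² = 0.5625. The share is 0.4375, about 52 of 120 (44%).
- Linear ramp over 6 months, then flat: the accrual area is 3 + 18 = 21 units, of which 6 fall in the last 6 months. 6/21 = 0.286, about 34 of 120 (29%).
- Rate falling linearly to zero: the share is (1 − 18/24)² = 0.0625, about 8 of 120 (6%).

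**Other accrual lengths, even accrual (6/T)**

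| T (months) | Share | Patients of 120 |
|---|---|---|
| 12 | 50% | 60 |
| 18 | 33% | 40 |
| 24 | 25% | 30 |
| 30 | 20% | 24 |
| 36 | 17% | 20 |

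**Primary outcome.** At 5 per month, taking 30 days to the month, a 48-hour window contains on average 5 × 2/30 = 0.33 patients and a 72-hour window 5 × 3/30 = 0.5. Early scores are therefore outstanding at the trigger for the last patient and hardly anyone else.

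**After correction.** If the study ends with the last patient's 6-month call, it closes at about 24 + 6 = 30 months from the start, and no call falls after the close.

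**The case against.** The strongest reply is that the sponsor plainly means to finish the calls. Sections 4.0 and 5.0 end participation only with the 6-month questionnaire, and Section 1.0 commits staff to trying to complete it. Section 9.0 can be read as loose wording for closing enrolment: it says what happens after 120 are enrolled, not that it happens at once. This carries weight. It makes the point a contradiction to be reconciled, not evidence that the calls will be dropped. It does not remove the contradiction, because no section gives a later end of study.

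A reader might infer three stronger things that the documents do not support.

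- That the protocol orders identifiers shredded at the 120th enrolment. It does not. Destruction is placed at the end of the study, with no date, and the link to the 120th enrolment comes only from joining that rule to another sentence of Section 9.0.
- That a quarter of the 6-month data will be lost. The 25% counts calls not yet due at the trigger, under an accrual pattern that the documents do not give.
- That the last patients' 24 to 72 hour scores will be missing from the analysis. That would require collection to cease within three days of the final enrolment, against the schedule in Sections 4.0 and 5.0. It is speculative.

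It is also fair to say that the consequence is limited. Section 7.0 does not list 6-month pain as an outcome, no hypothesis or sample-size statement depends on it, and Section 1.0 does not count a missed questionnaire as a deviation. That allowance covers calls that could not be completed, however. It does not cover calls that were never due before the study closed.

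**Conclusion.** The conflict is real and should be corrected. Section 9.0's end of study and the destruction rules in Sections 8.0 and 9.0 cannot be followed literally together with the 6-month call in Sections 1.0, 4.0 and 5.0.

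On the literal reading, 25% of patients would still be short of their call at the stop. This rests on even accrual, on the protocol's own 24-month estimate and on enrolment coinciding with surgery. The share is sensitive to the first two assumptions but is above zero in every scenario examined. What actually happens depends on which passage staff follow, and the documents do not settle that. The effect is confined to the 6-month aim.

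**What to change.** In Section 9.0, separate three milestones:

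1. Enrolment, not the study, stops at 120.
2. The study ends when the last patient's 6-month call has been completed or attempts to reach that patient have ended.
3. The 6-month data are analysed after that point.

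In both Section 8.0 (electronic and paper identifiers) and Section 9.0 (paper identifiers), tie destruction to the date in item 2. Changing Section 9.0 alone would leave the Section 8.0 rule without a clear date. The protocol defines no window for the call and no limit on attempts, so item 2 needs a short statement of when attempts count as ended.

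The 24 to 72 hour data may be analysed earlier, once the last patient's 72-hour data are in, so the primary analysis need not wait. This is optional and not needed to resolve the conflict.

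The cost is wording, and a formal study close about 6 months after the last enrolment. If the calls were always intended, that time is not new work. Treatment, sample size and assessments do not change.
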